6.2.2 Evaluations During Hospitalization Following ALB/Placebo Administration

Vital signs are monitored at a minimum of four times daily (q6h) through Day 7 or Discharge, whichever occurs first. Serum chemistry is collected at 24 (\pm 6 hours) and 48 hours (\pm 6 hours). All subjects must have a serum troponin drawn as part of the 24-hour (more frequently if clinically indicated) and 48-hour collections. Fluid balance (IV intake, output) data will be collected at 24 hours (\pm 6 hours) and 48 hours (\pm 6 hours). All subjects undergo a follow-up CT scan or brain MRI (including a minimum of diffusion-weighted imaging [DWI], gradient-echo [GRE], FLAIR, and intracranial MR angiography [MRA]) at 24 hours (\pm 6 hours) from the time of randomization. All subjects also undergo a clinical assessment of neurological and cardiological status at 24 hours (\pm 6 hours), 48 hours (\pm 6 hours), and 7 days (\pm 6 hours) or discharge, whichever comes first. This includes a NIHSS evaluation and standardized cardiac assessment. An EKG should be completed once during the 24-48 hour period. Both the baseline and 24-48h EKG must be reported centrally for review.

6.2.3 Intervention Discontinuation Evaluations

ALB infusion may be prematurely terminated if the subject exhibits an anaphylactic reaction or other adverse event thought to be related to ALB. Acute reactions to albumin therapy are rare and no such events occurred during the Albumin Phase 1 study. It is remotely possible that a transfusion reaction consisting of hypotension, urticaria and or laryngospasm in combination or as isolated symptoms may occur. Management of such events should be undertaken according to the best standard of care. Use of antihistamines, fluid and pressor agents and ACLS airway management may be required.

When a subject has been treated with thrombolysis, careful distinction should be made between reactions to thrombolysis and reactions to ALB. It is known that a small proportion (~1%) of stroke patients may suffer acute orolingual angioedema after thrombolysis treatment. This reaction occurs more commonly when patients are taking concurrent angiotensin converting enzyme inhibitors and when infarction involves the insula. (See Section 7.2) Rarely, subjects treated with thrombolysis may develop sudden isolated hypotension, possibly related to release of bradykinin induced by thrombolysis. Management is with volume replacement. Treatment with ALB in this setting may be protective. A call to the ALIAS Medical Monitor in this setting may be helpful.

6.2.4 Post-Intervention Evaluations

Subjects are followed for 1 year (12 months) from randomization. At 3 months* (\pm 14 days) post-randomization, each subject is required to come to the clinic for the determination of clinical outcome of the qualifying stroke – NIHSS, mRS, and BI. Outcomes are determined by a clinical investigator (physician or study coordinator) at the site who is certified to administer NIHSS and mRS, **AND** who is blinded to the subject’s admission treatment assignment, acute in-hospital course, and imaging data.

Subjects are also followed by telephone contact at 1 month* (\pm 7 days), 6 months* (\pm 14 days), 9 months* (\pm 14 days), and 12 months* (\pm 14 days) post-randomization.

At all contacts, data are collected on the subject’s current vital status, medical status, living arrangement, occurrence of AEs and/or SAEs; and, a mRS assessment is performed. In addition, all subjects complete the EuroQol [1] at 3 months and 12 months, the Questionnaire to Validate a Stroke-Free Status (QVSFS) [52] at 3, 6, 9, and 12 months, the Stroke-Specific Quality of Life (SS-QOL) [113,114] instruments at 3 months, and Trailmaking A and B at 3 months [125,126,127].

All efforts should be made to ascertain at least the vital status of subjects who are lost to follow-up prior to his/her 12-month follow-up date.

[*In this Protocol, “3 months” shall be defined as 90 days; “1 month” as 30 days; “6 months” as 180 days; “9 months” as 270 days; and, “12 months” as 365 days.]

6.2.5 Final Evaluations

At the 12-month anniversary date (\pm 14 days) of each subject’s randomization date, the study coordinator, or other designated personnel, contacts the subject via telephone to evaluate mRS, EuroQol, QVSFS, follow-up status, new SAEs and unresolved previously reported SAEs since the last contact, and to complete the end-of-study CRF. If a subject dies prior to that date, the end of study/death CRFs must be completed. The study coordinator, or other designated personnel, should get as much information as possible regarding the date, time, and circumstances of the subject’s death.

6.3 Off-Intervention Requirements

All subjects are followed using the intent-to-treat principle. Thus, regardless of whether or not a subject has completed the study intervention or received the study drug, all follow-up procedures will be performed according to the standard schedule. The best standard of care applies to all subjects.

7. CLINICAL MANAGEMENT OF ADVERSE EXPERIENCES

7.1 Complications of ALB Therapy

The major concern with ALB therapy is volume overload. ALB has oncotic properties and therefore draws sodium and water into the intravascular space. Subsequently ALB redistributes in total body water. Administration of ALB at higher doses in the Phase I Trial resulted in a 1.5 to 2 g/dL (15-20 g/L) increase in plasma albumin levels at 4 hours post-administration. The overall

incidence of clinical signs of CHF was approximately 13%, but in each case it was mild and the subjects responded to a maximum of 2 doses of furosemide.

Other potential cardiac complications of ALB therapy include atrial arrhythmias (e.g., atrial fibrillation/flutter) and possible myocardial ischemia. Volume infusion may promote atrial wall stress due to stretching, which could lead to atrial arrhythmias. A similar mechanism may occur, causing ischemia. Myocardial wall stress is associated with greater metabolic demand, which may not be available in a subject with coronary stenoses, as many stroke subjects may have. Further, the vast majority of stroke patients are chronic hypertensives, and such patients already tend to have reduced myocardial compliance.

Note that myocardial distress may occur, as shown by evidence of slightly elevated troponins, in up to 20% of ischemic stroke subjects, even without evidence of a true acute coronary syndrome. Thus, it is important to make a clear distinction between subjects who have troponin elevation due to an acute coronary syndrome and troponin elevation without acute coronary syndrome. The latter may be caused by the stroke and is presumed to arise by the same mechanism as seen in acute sub-arachnoid hemorrhage. Stroke may cause a catecholamine surge, possibly due to involvement of the insula, resulting in subendomyocardial damage.

7.2 Complications of Thrombolytic Therapy

Intracranial hemorrhage (ICH): ICH is a known complication of thrombolytic therapy. Symptomatic ICH was observed in one subject in the Albumin Phase I Trial. Among subjects who are treated with IV thrombolysis, symptomatic ICH occurs in about 6% of subjects. Thrombolytic-related ICH generally occurs in the first 6 hours after thrombolytic therapy. The acute management of intracranial hemorrhage consists of the following:

- Immediate discontinuation of thrombolysis.
- Consider administration of cryoprecipitate, fresh frozen plasma, and platelets; there is no proof, however, that this empiric therapy results in an altered outcome.
- Subjects who concomitantly receive cryoprecipitate, fresh frozen plasma, platelets and ALB may be at particular risk of developing volume overload. These subjects should be managed, as needed, with additional furosemide to prevent the development of acute respiratory failure due to pulmonary edema.

Systemic hemorrhage: Systemic hemorrhage is an uncommon complication of thrombolytic therapy, occurring in less than 0.5% of patients. ALB administration was not shown to be a predictor of systemic hemorrhage in the Albumin Phase I Trial. Management is similar to ICH, and precautions against volume overload should be taken as discussed in Section 7.1.

Orolingual angioedema: Orolingual angioedema is an uncommon complication of thrombolytic therapy, occurring in 1% or less of subjects treated with thrombolysis. There is no known relationship between ALB therapy and angioedema. Risk factors for angioedema include the premonitory use of ACE inhibitor, β -blockers, and fronto-insular infarction [59]. Management of orolingual angioedema varies by severity. Most angioedema is mild and does not require treatment. Management with antihistamines (50mg IV diphenhydramine and 50mg IV ranitidine) may suffice. For more severe cases, 50mg IV hydrocortisone may be administered. Racemic epinephrine is not advised with thrombolysis because of the potential risk of inducing intracerebral hemorrhage. Early consultation with anesthesia for airway management should be considered for more severe cases

Acute hypotension: Acute hypotension is an uncommon occurrence with thrombolytic therapy, occurring in 0.4% of patients. It may be related to release of bradykinin. This effect was not observed in the Albumin Phase I Trial. Treatment is generally successful with simple volume expansion, and, therefore, ALB may be protective [123]. In more severe cases, use of inotropic agents (e.g., Dobutamine) may be appropriate.

8. ADVERSE EVENTS REPORTING

8.1 Definition of Adverse Events

An *adverse event* is defined as any untoward event or complication that was not previously identified, or that occurs with greater frequency or severity than previously reported, which occurs during the protocol intervention or during the follow-up period, whether or not considered related to the protocol intervention. Abnormal laboratory findings considered by the reporting physician to be clinically significant are included as adverse events. The investigator, on the basis of his or her clinical judgment and the following definitions, determines the relationship of the adverse event to the protocol intervention as one of the following:

Definite: Causal relationship is certain (i.e., the temporal relationship between drug exposure and the adverse event onset/course is reasonable; there is a clinically compatible response to dechallenge; other causes have been eliminated; and the event must be definitive pharmacologically or phenomenologically, using a satisfactory rechallenge procedure if necessary).

Probable: High degree of certainty for causal relationship (i.e., the temporal relationship between drug exposure and the adverse event onset/course is reasonable; there is a clinically compatible response to dechallenge [rechallenge is not required]; and other causes have been eliminated or are unlikely).

Possible: Causal relationship is uncertain (i.e., the temporal relationship between drug exposure and the adverse event onset/course is reasonable or unknown; dechallenge/rechallenge information is either unknown or equivocal; and while other potential causes may or may not exist, a causal relationship to the study drug does not appear probable).

Unlikely: Not reasonably related, although a causal relationship cannot be ruled out (i.e., while the temporal relationship between drug exposure and the adverse event onset/course does not preclude causality, there is a clear alternate cause that is more likely to have caused the adverse event than the study drug).

Not related: No possible relationship (i.e., the temporal relationship between drug exposure and the adverse event onset/course is unreasonable or incompatible; or a causal relationship to study drug is implausible).

Adverse events are further graded as mild, moderate, severe, life-threatening, or fatal. Adverse events that are non-serious must be followed through the 3-month follow up visit. Only serious adverse events are reported beyond the 3-month follow up visit.

An **unexpected adverse event** is any event for which the specificity or severity is not consistent with the current investigator brochure; or, an adverse event for an individual subject that may be adjudicated to be “unexpected” in view of the severity, the timing, and/or the medical context in which it occurs. The study site PI should take all factors carefully into account in deciding whether he/she believes that the event is expected or unexpected.

A **Serious Adverse Event (SAE)** is one that results in any of the following outcomes:

- death due to any cause;
- a life-threatening adverse experience (i.e., the subject was at immediate risk of death from the event as it occurred);
- in-patient hospitalization or prolongation of existing hospitalization. (Hospitalizations scheduled before enrollment for an elective procedure or treatment of a pre-existing condition that has not worsened during participation in the study is not considered a serious adverse event);
- a persistent or significant disability/incapacity (i.e., a substantial disruption of one’s ability to conduct normal life functions);
- a congenital anomaly/birth defect;
- an important medical event that may not result in death, be life-threatening, or require hospitalization, but may jeopardize the subject and may require medical or surgical intervention to prevent one of the outcomes listed in this definition. Any new diagnosis of cancer (made after study enrollment) is considered an important medical event.

For the ALIAS Trial, **severe, or life-threatening** pulmonary edema or CHF (as defined in Section 8.2) occurring within 48 (\pm 6) hours of randomization is considered a SAE. All serious adverse events must be followed for the duration of the 12-month trial or until resolution, whichever comes first.

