8.4 Reporting of Adverse Events and Serious Adverse Events

In order to assure prompt and complete reporting of adverse events or complications, all non-serious AEs occurring through the 3-month follow-up visit and all serious AEs occurring through the 12-month follow-up visit are recorded in the WebDCU™ system.

For each AE, the clinical site staff records the event in WebDCU™, providing relevant information such as the AE description, the dates of onset and resolution, severity, and seriousness. For SAEs, they also must provide the suspected relationship to stroke, suspected relationship to thrombolysis, suspected relationship to the study drug, and a narrative description of actions taken as a result of the SAE.

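### Section 8.1 defines an adverse event by novelty or excess over earlier reports, which contradicts Sections 8.2, 8.3 and 8.8 and leaves recording of some known non-serious events to each site's reading

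*Protocol*

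**What the plan says.** The general definition in Protocol Section 8.1 covers "any untoward event or complication that was not previously identified, or that occurs with greater frequency or severity than previously reported", arising during the intervention or follow-up, "whether or not considered related to the protocol intervention". A further sentence adds laboratory values: "Abnormal laboratory findings considered by the reporting physician to be clinically significant are included as adverse events".

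The same section then defines an unexpected adverse event separately, as "any event for which the specificity or severity is not consistent with the current investigator brochure" (or one adjudicated unexpected for the individual subject). It lists the criteria for a serious adverse event, beginning with "death due to any cause".

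Section 8.4 sets the recording duty: sites enter "all non-serious AEs occurring through the 3-month follow-up visit" and serious events through 12 months. Under Section 8.7 those records go in aggregate to the DSMB and in annual reports to the regulators.

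Section 8.2 gives formal definitions of selected adverse events, Section 8.3 defines intracranial and systemic hemorrhage, and Section 8.8 lists ten events to be monitored. None of these applies a test of novelty or of excess frequency.

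**The concern.** Novelty and excess frequency are part of the definition that decides what sites enter under Section 8.4. Taken at its word, the definition excludes a complication that has been identified before and occurs at its reported rate and severity. The clause on relatedness lifts only the causality condition, and the laboratory sentence adds no clinical events.

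Frequency relative to earlier reports is also a property of pooled data. An investigator with one blinded subject cannot assess it.

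At stake is the comparison of non-serious harms between arms. It is interpretable only if sites record the same kinds of event in the same way. The synopsis plans about 100 centers. If some follow Section 8.1 and others Section 8.2, recording will be uneven, and events never entered may not be recoverable later.

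**Working it through.** The Protocol states no figure that depends on this definition, so there is none to reproduce. The check is a comparison of texts, followed by simple arithmetic for scale.

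**Step 1: does the rest of Section 8 follow the Section 8.1 limit?**

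- *Unexpected adverse event (8.1).* It is a sub-class of adverse event, so expected adverse events must exist. The general definition leaves little or no room for them.
- *Serious adverse event (8.1).* Death from any cause, and severe or life-threatening pulmonary edema or heart failure within 48 (±6) hours, qualify with no novelty test.
- *Section 8.2.* It names known albumin complications (heart failure from asymptomatic upward, coronary events, enzyme leak, allergic reaction, atrial fibrillation and flutter) and known stroke complications (neurological deterioration, pneumonia, venous thromboembolism, urinary infection and others). Only fibrillation and flutter carry an explicit statement that any post-treatment occurrence counts.
- *Section 8.3.* It defines symptomatic and asymptomatic intracranial hemorrhage and systemic hemorrhage.
- *Section 8.8.* It monitors ten events, including shortness of breath, symptomatic and asymptomatic intracranial hemorrhage, and death. Heart failure is listed only when severe or life-threatening.

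So Section 8.1, read literally, contradicts the sections that follow it, and no sentence says which governs.

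**Step 2: which known events depend on the reading chosen?**

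- *Protected whatever the reading:* deaths, atrial fibrillation and flutter, symptomatic and asymptomatic intracranial hemorrhage, severe or life-threatening heart failure, and the other Section 8.8 events.
- *Dependent on Section 8.2 prevailing:* non-serious events named there but not in Section 8.8 and without an explicit rule. The clearest is mild or moderate heart failure. Section 7.1 calls volume overload the major concern, gives about 13% with clinical signs in Phase I, and adds that "in each case it was mild and the subjects responded to a maximum of 2 doses of furosemide". That is an identified event of known frequency and severity.
- *No second route:* known non-serious events named in none of Sections 8.2, 8.3 or 8.8. Mild orolingual angioedema, described in Section 7.2, is an example.

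**Step 3: scale, from the Protocol's own rates.**

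- Angioedema: at most 1% of thrombolysis subjects (Section 7.2); about 880 anticipated (Section 10.4.1). 0.01 × 880 = 8.8, so at most about 9 subjects over both arms, if every case were non-serious and omitted.
- Symptomatic hemorrhage: about 6% with IV thrombolysis (Section 7.2). 0.06 × 880 = 52.8, about 53. These stay captured through Sections 8.3 and 8.8.
- Heart failure signs on albumin: 0.13 × (1,100 / 2) = 71.5, about 72 subjects at the Phase I rate. This shows how common the event may be. It is not a count of lost events, because Section 8.2 names the event and the Protocol gives no omission rate.

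**The case against.** A reader might infer that known albumin and stroke complications are simply not adverse events in this trial, and might go on to estimate how many heart failure events would be lost. The Protocol supports neither inference. Section 8.2 names heart failure down to its asymptomatic and mild grades, along with many stroke complications. Related information is also collected outside adverse event reporting: cardiac examinations at 24 hours, 48 hours and day 7 or discharge, a fluid and diuretic form (Section 6.1), evaluation for respiratory compromise through 24 hours (Section 5.3.1), and shortness of breath by treatment group (Section 8.8). Any assumed omission percentage would have no basis in the document.

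It can also be argued that the Section 8.1 sentence is meant at subject level: new in this subject, or worse than this subject's prior condition. That would fit Sections 8.2 and 8.8, and the exclusion from serious events of scheduled hospitalizations for a pre-existing condition that has not worsened. The reading is possible, but the sentence does not say so, and its reference to previously reported frequency points at least as naturally to earlier experience with the treatment. If the subject-level meaning was intended, the sentence needs rewording to state it.

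What stands of the objection is the limit on consequences. What it does not remove is the contradiction, or the fact that the back-up forms are not adverse event records and that mild and moderate heart failure appears neither in the serious-event rule specific to this trial nor, under that name, in Section 8.8.

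**Conclusion.** The point holds as an internal contradiction in an operative definition. Section 8.1, read literally, imposes a test that a site cannot apply and that Sections 8.2, 8.3 and 8.8 disregard, without saying which text prevails.

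The exposure is limited to two things: uneven recording between sites of non-serious events that rely on Section 8.2 alone, and possible omission of known non-serious events named in none of the three sections. For the angioedema example the ceiling is about 9 of 880 subjects, assuming the 4:1 recruitment ratio behind the 880, the 1% upper rate, and that every case is non-serious and left out. The size of any uneven recording of heart failure cannot be derived from the Protocol.

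The primary efficacy outcome (Section 10.2.1), the 30-day mortality outcome and its stopping guideline (Sections 10.2.3 and 10.7.2), and the events monitored under Section 8.8 do not depend on this wording. The correction should still be made: a site that followed the stated rule would wrongly leave out known events.

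**What to change.** Replace the general definition in Section 8.1 with a sentence to this effect: an adverse event is any untoward occurrence, or worsening of a condition present at baseline, in a randomized subject after randomization, whether or not it is expected, previously reported or considered related to the intervention. Keep the laboratory sentence. Leave expectedness to the existing definition of an unexpected adverse event, where it serves expedited reporting.

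Add the new sentence to the site training material so that all centers apply it alike. Sections 8.2, 8.3, 8.4 and 8.8 then agree with Section 8.1 without further change.

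The cost is one sentence, a training note and slightly more events to record. Treatment, outcomes, sample size and analyses are unchanged.

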8.2 Formal Definitions of Selected Adverse Events

Acute Congestive Left Heart Failure/Pulmonary Edema. Acute CHF is defined as pulmonary edema occurring within 48 (\pm 6) hours of randomization. Pulmonary edema is characterized by all of the following: (a) supplemental oxygen requirement or an increase in oxygen requirement with associated fall in SaO₂; (b) elevated respiratory rate and tachycardia; (c) physical examination evidence of pulmonary congestion including elevated jugular venous pressure, presence of hepatjugular reflux, pulmonary auscultatory rales or wheezing.

Although a CXR is not required for diagnosis, if one is done and shows radiological evidence of pulmonary edema it will support the diagnosis.

Acute CHF/pulmonary edema is further classified as:

- (i) Asymptomatic – the subject requires no additional therapy. Pulmonary congestion may be only shown on CXR in this case.

- (ii) Mild – the subject requires and responds to the single mandated dose of a diuretic and requires supplemental oxygen via nasal prongs only. A single dose of diuretic shall be considered 20mg of intravenous furosemide.
- (iii) Moderate – the subject requires more than the mandatory dose of a diuretic but responds and requires supplemental oxygen via nasal prongs only.
- (iv) Severe – the subject requires treatment with multiple doses of diuretic, supplemental oxygen via face mask, or additional problems arise such as cardiac arrhythmias and cardiac telemetry is required.
- (v) Life-threatening – the subject requires intubation or non-invasive BiPAP/CPAP to manage significant hypoxemia.

Acute coronary syndrome (MI). Elevated cardiac-specific CK (total CK-MB mass), troponin-T, or troponin-I greater than the upper limit of normal (ULN) at the clinical site **plus** clinical symptoms or EKG evidence of myocardial injury (ST deviation ≥ 1 mm in 2 contiguous leads or new/previously undocumented Q waves). [120]

Myocardial injury without acute coronary syndrome -- “enzyme leak”. Elevated cardiac-specific CK (total CK-MB mass), troponin-T, or troponin-I greater than the upper limit of normal (ULN) at the clinical site in the absence of clinical symptoms or EKG evidence of an acute coronary syndrome.

Acute coronary syndrome - unstable angina. Clinical symptoms (chest pain, dyspnea) or EKG evidence (ST depression or T wave inversion) of reduced myocardial flow without a significant elevation in cardiac enzymes. [120,121]

Allergic reaction to ALB. Type I allergic reaction (anaphylaxis) manifesting as hives, laryngospasm, bronchospasm, hypotension (distributive shock).

Atrial fibrillation (AF). Supraventricular tachyarrhythmia characterized by uncoordinated atrial activation with consequent deterioration of atrial mechanical function. [122] Described on the EKG by the replacement of consistent P waves by rapid oscillations or fibrillatory waves that vary in size, shape, and timing, associated with an irregular, frequently rapid ventricular response when atrioventricular (AV) conduction is intact.[122] Any atrial fibrillation occurring post-treatment is considered an adverse event.

Atrial flutter. A more organized arrhythmia than AF and is characterized by a saw-tooth pattern of regular atrial activation called flutter (*f*) waves on the EKG, particularly visible in leads II, III, and aVF (inferior limb lead on a 12-lead EKG), without an isoelectric baseline between deflections.[122] Any atrial flutter occurring post-treatment shall be considered an adverse event.

Bowel pseudo-obstruction. Failure of peristalsis of the large bowel with associated dilatation. May result in sepsis and toxic megacolon.

Constipation. Hard, infrequent bowel motions. May be functionally defined as no bowel motion for 5 or more days.

Deep vein thrombosis (DVT) or pulmonary thrombo-embolism (PE). DVT and PE are spectrums of the same disease. A DVT is a thrombotic occlusion of a large vein in the leg, pelvis, abdomen, or arm. A PE is a thrombotic occlusion of a pulmonary artery, most often due to a venous embolus from a DVT.

Hemicraniectomy. Removal of a large ovoid region of the skull performed with an associated duroplasty to allow infarcted brain to swell without causing rostral-caudal deterioration and death.

Sudden vascular death. Deaths are categorized as sudden cardiovascular if they are unexpected, rapidly follow symptoms, and are attributable to a cardiovascular or unexplained cause. [122]

Pulmonary hypertension. (A) Measured (e.g., Swann-Ganz catheter) or estimated (echocardiography) right ventricular end-diastolic pressure greater than 10 mm Hg; or (B) Measured or estimated using echocardiography, a peak right ventricular systolic pressure > 25mm Hg.

Renal failure. Renal failure shall be defined as renal dysfunction requiring artificial renal replacement therapy (hemodialysis or peritoneal dialysis).

Renal insufficiency. Renal insufficiency shall be defined as renal dysfunction, shown by a 20% increase in serum creatinine from baseline, not requiring renal replacement therapy.

Urinary tract infection (lower). Bacterial infection of the bladder, often as a complication of Foley catheter placement. Should be suspected based upon the presence of white cells and/or nitrites in the urine and proven by culture.

Respiratory failure. Hypoxemia or hypercarboxemia requiring mechanical ventilation (either intubation or non-invasive with BiPAP/CPAP).

Respiratory insufficiency. Hypoxemia or hypercarboxemia that can be managed without mechanical ventilation (either intubation or non-invasively with BiPAP/CPAP).

Acute treatment-emergent hypertension. Elevated blood pressure occurring in the first 48 hours of 220 systolic or 120 mmHg diastolic, OR an increase of 20% in either systolic blood pressure or mean arterial pressure over baseline values.

Increased intracranial pressure. Raised ICP (> 25 cm H₂O) requiring interventional treatment (e.g., hemicraniectomy, placement of an external ventricular drain).

Neurological deterioration. Any increase in NIH stroke scale of 4 points or more, over the baseline value, occurring at any point between randomization and 48 hours.

Stroke death. Death from stroke (neurological death attributed to the stroke) within 7 days (\pm 6 hours) or during hospitalization for the qualifying stroke.

Recurrent stroke. A new stroke occurring in a new vascular territory, separated in time from the initial stroke event by 48 hours or more.

Progression of stroke. Worsening of the same stroke symptoms that defined the initial stroke event, involving deficits attributable to the same vascular territory and occurring within 48 hours of the original stroke event.

Pneumonia. The following criteria define pneumonia:

- (i) hypoxemia ($S_aO_2 < 90\%$)
- (ii) pulmonary air space disease defined by clinical examination and/or chest X-ray
- (iii) fever (temperature $> 38^\circ C$)

Two of three are required. Cough, dyspnea, pleuritic chest pain and delirium are additional supportive symptoms/signs. Pneumonia is confirmed by culture of a single bacterial or viral organism or by clinical resolution of symptoms with antimicrobial treatment and absence of a good alternate diagnosis (e.g., pulmonary embolus, atelectasis, congestive heart failure).

Hypotension. Hypotension is defined as the syndrome of low blood pressure with SBP < 85 mmHg.

Treatment-emergent hypotension. Hypotension associated with clinical/radiographic/laboratory evidence of end-organ dysfunction. This could include, but is not limited to:

- delirium or reduced level of consciousness, or focal neurological signs indicating brain dysfunction
- symptoms and signs of an acute coronary syndrome indicating cardiac dysfunction
- significantly reduced urine output ($< 15cc/h$) indicating renal dysfunction
- significantly elevated liver enzymes indicating shock liver/hepatic dysfunction

(NOTE: Extra care should be paid to blood pressure monitoring in subjects on ACE inhibitors.)

Hypercarbia. Hypercarbia (in the context of respiratory failure/insufficiency) is defined as an arterial $pCO_2 > 45$ mmHg.

